8 ANALYSIS POPULATIONS

There will be one analysis population in this trial:

Safety population: The safety population will include all patients who have received at least one dose of study treatment.

9 STUDY PATIENT

9.1 Patient Disposition

All patients who provide informed consent will be accounted for in this study. The number of patients screened and number and percentage who failed screening (screen failures) will be presented. The reason for screen failure (count and percentage) will be presented for all screened patients who failed screening, if applicable. Moreover, the number of patients enrolled (patients will be considered as enrolled if they started Day 1) and included in the safety population will be presented. Study completion status and the reason for study discontinuation, including if related to COVID-19 or not, will also be presented both as count and percentages. The percentage of patients with screen failures will be calculated using the number of patients screened as denominator. The percentage of screen failure by reasons will be calculated using the number of screen failures as denominator. The percentage of patients with study discontinuation and reasons for discontinuation, including if related to COVID-19 or not, will be calculated by reasons using the number of enrolled patients who did not complete study as denominator. Otherwise, percentages will be calculated using the number of patients enrolled as denominator.

Number of days in the study will be calculated as follows and summarized using descriptive statistics based on the safety population:

$$\text{Number of days in study} = \text{Date of completion/discontinuation} - \text{first study drug dose date} + 1.$$

A listing of patients' disposition will be provided. A listing of patients excluded from the safety population and associated reason, and a listing of missed visits due to the COVID-19 pandemic will also be provided.

9.2 Protocol Deviation

All protocol deviations will be reported based on Almirall protocol deviations categories. Important vs. not important classification of protocol deviations will be conducted prior to the database lock.

The number of events and the number and percentage of patients with at least one important protocol deviation will be summarized by deviation category and sub-category using the safety population. In case of a site-level protocol deviation, one protocol deviation for each patient for that site will be accounted for in the tables and listings. The number of events and the number

M-14867-32

Statistical Analysis Plan Status: Version (17 Jan 2023)

and percentage of patients with at least one protocol deviation related to COVID-19 will be summarized similarly.

A listing of all protocol deviations will also be provided.

10 DEMOGRAPHIC AND OTHER BASELINE CHARACTERISTICS

10.1 Demographics and Baseline Characteristics

Descriptive statistics will be used to summarize demographic characteristics (age as collected at the time of Informed Consent Form, sex, Fitzpatrick skin type, race, and ethnicity) and baseline characteristics (height, body weight, area of face or scalp treated, number of AK lesions in the treatment field, presence of scarring, hypopigmentation and hyperpigmentation in the treatment field, and smoking and alcohol habits usage [never, current or former for smoking; consumption yes vs no for alcohol]), based on the safety population. Patients who reported more than one race will be summarized as 'Multiple' races in the table, and all races selected will be displayed in the listing.

A listing of all demographics and baseline characteristics will be provided.

10.2 Medical History

Surgical and medical history will be coded according to the Medical Dictionary for Regulatory Activities (MedDRA), Version 25.0.

Non-AK surgical and medical history will be summarized by system organ class (SOC) and preferred term (PT) using the safety population. A patient who experienced the same non-AK surgical and medical history event multiple times will be counted only once for the corresponding PT. Similarly, if a patient experienced multiple non-AK surgical and medical history events within the same SOC, the patient will be counted only once for that SOC. Non-AK surgical and medical history events will be sorted alphabetically by SOC and within each SOC the PT will be presented by decreasing order.

A listing of all non-AK surgical and medical history events will be provided.

AK disease history, including body parts and sides affected, will be summarized based on the safety population. The time since first AK diagnostic (in years) will be calculated as:

Time since first AK diagnostic (years) = {[First study treatment dose date – first AK diagnostic date] + 1} / 365.25.

Should any AK diagnostic date be partially or completely missing, the time since first AK diagnostic will be left as missing.

M-14867-32

Statistical Analysis Plan Status: Version (17 Jan 2023)

A listing of AK disease history will be provided.

11 EXPOSURE AND COMPLIANCE

11.1 Exposure to Study Medication

Duration of exposure to study treatment, in days, will be computed as follows:

$[(\text{Date of last dose of study treatment} - \text{Date of first dose of study treatment}) + 1]$.

Descriptive statistics for the duration of exposure to study treatment will be presented based on the safety population. Duration of exposure will also be presented by treatment area (scalp or face) sub-groups.

A summary of amount of product applied will be presented based on the safety population. Amount of product applied will be derived based on the information on the pre-dose packets weight and post-dose packets weight captured in the eCRF. Amount applied (in grams) will be computed as follows:

$(\text{Sum of packets weight pre-dose on Day 1} - \text{Sum of packets weight post-dose on Day 5})$.

If the information on packet weight is missing for a dispensed packet (i.e., the number of packets returned is not equal to the number of packets dispensed), the amount applied will be missing.

A listing of study treatment amount applied, number of packets dispensed, returned and used will be provided.

11.2 Compliance with Study Medication

Compliance with study treatment (%) will be calculated based on used packets as follows:

$$\frac{\text{Total number of used packets per the eCRF}}{\text{Total duration of exposure (days)} \times \text{Planned number of dose per day (i.e., 1)}} \times 100$$

M-14867-32

Statistical Analysis Plan Status: Version (17 Jan 2023)

Descriptive statistics for the compliance to study treatment will be presented based on the safety population. Frequency distribution will also be presented for the following compliance categories: <80%, 80% to 120%, >120%. Compliance will also be presented by treatment area (scalp or face) sub-groups.

If a patient did not return the full number of packets dispensed, his compliance will be left as missing.

A listing of patient exposure, compliance and drug interruption will be provided.

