## **5.2 Summary of the Known Potential Risks and Benefits**

Actinic keratosis is a UV light-induced pre-cancerous lesion of the skin that represents the initial clinical manifestation of intra-epidermal abnormal keratinocyte proliferation. Given the demonstrated potential for progression to SCC, dermatologists generally encourage and actively pursue treatment, with a goal of completely eliminating AK lesions, thereby reducing the risk of progression to invasive SCC.

Data from the two pivotal Phase 3 studies demonstrate that treatment with tirbanibulin ointment 1% once-daily for 5 days is effective in the treatment of AK of the face or balding scalp.

In the pivotal studies, the safety profile of tirbanibulin ointment 1% showed a low rate of treatment-emergent AEs and no unexpected or unanticipated safety findings. The overall incidence of treatment-emergent AEs (TEAEs) was similar between the tirbanibulin ointment 1% and vehicle groups, and there were no treatment-related treatment-emergent serious AEs (TESAEs) or discontinuations due to a TEAE. There were also no long-term safety concerns related to tirbanibulin ointment 1% in patients followed up to 1 year after Day 57.

The most frequently reported local tolerability signs were transient, mild to moderate erythema and flaking/scaling. Treatment-related AEs were mostly transient, mild to moderate application-site pruritus or pain, and most did not require treatment.

The safety profile of tirbanibulin ointment 1% observed in the Phase 1 maximal-use trial M-14687-01, in which study drug was applied to 100 cm^2 on the face or balding scalp, was consistent with that observed in the pivotal studies.

Based on the available efficacy and safety data from the completed clinical and nonclinical studies, the benefit-risk assessment is positive and supports the evaluation of tirbanibulin ointment 1% in this Phase 3 study of patients with AK of the face or scalp.

Further information regarding the nonclinical and clinical characteristics, summaries of the known and potential risks, as well as reasonably expected adverse reactions of the product under investigation, is provided in the Athenex KX2-391 (tirbanibulin) Investigator's Brochure.

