#### **8.4 Treatment Discontinuation Criteria**

Any patient may discontinue from study treatment at any time during the trial at the discretion of the Investigator or at the request of the patient. For patients who discontinue treatment, efforts should be made to encourage the patient to remain in the trial and complete the trial-related assessments. The main reason for such a premature treatment discontinuation must be documented in the electronic case report form (eCRF), as follows:

- Adverse event: If a patient experiences an AE, treatment discontinuation will be at the discretion of either the Investigator or the patient regardless of the causal relationship to the investigational medical product (IMP).
- Protocol deviation: Any protocol deviation detected should be corrected when possible and the patient should be allowed to continue. ONLY the following deviations should lead to treatment discontinuation: those which could affect patient's safety (eg, illness requiring treatment(s) which in the clinical judgement of the Investigator [or after discussion with the trial monitor] might invalidate the trial by interfering with the IMP) or which are due to patient unwillingness to comply with the trial activities or those violations of inclusion and/or exclusion criteria detected
- Lost to follow-up: Non-attendance. In these cases, every effort should be made by the Investigator to ascertain the reason and to assure patient's attendance as soon as possible. Every effort (at least three documented attempts) should be made to contact the patient and documented in the medical records. If patient cannot be reached after that, a registered mail letter will be sent to the patient and documented in the medical records
- Patient's personal request: The patient is permitted to stop his/her treatment at any time during the trial without incurring any loss in his/her medical care. The Investigator should ensure that such discontinuation is not due to an AE or disease exacerbation, in which case the corresponding reason should be recorded
- Pregnancy

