#### **9.4 Treatment Administration**

Treatment will begin on Day 1, following confirmation of patient eligibility and collection of all pre-dose samples and assessments.

At Baseline (Day 1 pre-dose), the Investigator will confirm the TF on the face or balding scalp that was identified at Screening and the patients will receive instructions on how to apply the topical medication and how to care for the TF.

Patients will be provided with 5 single-dose packets containing tirbanibulin ointment 1%.

The first dose will be administered by the patient under the supervision of study personnel on Day 1 at the site. The patient will self-administer the remaining single-dose packets once daily at home for the next 4 consecutive days. The fifth dose should be applied by the patient at home before the Day 5 site visit.

Tirbanibulin ointment 1% will be applied to cover the treatment field of approximately 100 cm^2, corresponding to approximately 0.5% of the body surface area. Study medication should be applied each day at approximately the same time. The treatment field should not be wet, should be kept dry for approximately 8 hours after application, and should not be touched or covered with dressing. The ointment should not be applied near the eyes, mouth, or lips.

Patients will return the used medication packaging (all parts of each packet, including the torn opening part) and any unused study medication back to the clinical site at the next visit to check compliance and for drug reconciliation purposes. Further details will be given in the study manuals (see Section 9.5).

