Weight of study drug packets ^f		X			X				
Standardized photography of the treatment field	X	X ^{a,l}			X	X	X	X	X
AEs ^g	X	X	X		X	X	X	X	X ^h

M-14867-32

Statistical Analysis Plan Status: Version (17 Jan 2023)

Period	Screening*	Treatment		Response Assessment					
		1	2	At home, once-daily self-administration ^m	3	4	5	6	7
Visit(s)									ET/EoS
Day(s)	-28 to -1		1 (Baseline)	2 to 5	5	8	15	29	57
Visit Time Window (days)	None	None			None	±2	±2	±3	±3
Treatment Field location		X ^a		X	X	X	X	X	X
Focused dermatological exam of treatment field									
Local tolerability		X ^a			X	X	X	X	X ^b
Hypo- and hyperpigmentation and scarring		X ^a			X	X	X	X	X ^b
AK Lesion count in the TF	X	X			X	X	X	X	X

Abbreviations: AE=adverse event; AK=actinic keratosis; ECG=electrocardiogram; ET=Early Termination; EoS=End of Study; ICF=informed consent form; TF=treatment field; WOCBP=women of child-bearing potential.

* Patients who require a washout period from prohibited concomitant treatments should be seen and sign the ICF prior to the Screening visit, to ensure the necessary washout before starting treatment. No trial assessments will be performed on that date and the Screening visit will be scheduled according to the washout length required for the specific medication stopped.

^a Assessments/procedures performed before treatment administration. Day 1 evaluation will serve as a Baseline for these assessments.

^b Patients must be in a supine position for 5 minutes prior to ECG.

^c Highly sensitive urinary pregnancy test performed at the clinical trial site.

^d Physical examination to include height, weight, and an assessment of head, eyes, ears, nose and throat, integumentary/dermatological, gastrointestinal, cardiovascular, respiratory, musculoskeletal, neurological systems, and an expanded dermatological examination to cover the sun-exposed areas, where photo-damage is likely. Height is measured only at screening.

M-14867-32

Statistical Analysis Plan Status: Version (17 Jan 2023)

^e On Day 5 patients are to bring all 5 study drug packets back to the site (used and unused) with their respective torn parts in the individual closed zipper storage bag provided in the study kit.

^f All study drug packets will be weighed together in their respective closed zipper storage bag before and after use (including the torn opening part).

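### The SAP's compliance formula scores a patient who stops treatment early, without missed days, as 100% compliant

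*SAP*

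**What the plan says.** SAP 11.2 defines compliance as the number of used packets recorded in the eCRF, divided by "Total duration of exposure (days" times one planned dose per day, times 100. The duration comes from SAP 11.1 ("Duration of exposure to study treatment, in days, will be computed as follows"): date of last dose minus date of first dose, plus 1. Both dates are the patient's own.

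The result is summarised overall and by face or scalp. The SAP adds: "Frequency distribution will also be presented for the following compliance categories: <80%, 80% to 120%, >120" per cent. One exception applies: "If a patient did not return the full number of packets dispensed, his compliance will be left as missing".

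The course itself is fixed. Patients apply the ointment once daily for 5 days (SAP 3.2) and receive 5 single-dose packets (protocol 9.4). Footnote e of the SAP schedule of assessments covers the return: "On Day 5 patients are to bring all 5 study drug packets back to the site (used and unused", in the footnote's words. Protocol 9.5 says that compliance is assessed by counting packets but names no denominator.

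**The concern.** When a patient doses daily and then stops for good, the numerator and the denominator shrink together and the ratio stays at 100%. It detects only gaps before the last dose. That is adherence while on treatment, yet the SAP labels it compliance with study treatment.

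The missing-data rule does not remove the problem in the planned case. Patients are asked to return every packet, and protocol 8.4 tries to keep those who stop treatment in follow-up: "For patients who discontinue treatment, efforts should be made to encourage the patient to remain in the trial and complete the trial-related assessments".

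At stake is how the compliance tables are read. Patients who used 1, 2 or 3 of 5 packets would sit in the same category as those who completed the course, so a reader would overestimate how much of the course was applied. In a trial whose primary objective is safety and tolerability on a larger field, a permanent stop is the departure from the regimen most directly tied to tolerability, and this measure cannot register it.

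**Working it through.** The documents give no numerical compliance result to reproduce, so the check evaluates the formula directly.

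**Inputs.** Used packets, k (SAP 11.2). Duration D = last dose date − first dose date + 1 (SAP 11.1). Planned doses, 5 (SAP 3.2; protocol 9.4). Categories and missing rule (SAP 11.2).

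**Formulas.** SAP compliance = k / (D × 1) × 100. Planned-dose compliance = k / 5 × 100.

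**Gap-free stop after k doses, one packet a day, all 5 packets returned.** Here D = k.

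| Doses taken | SAP | SAP category | Planned-dose | Planned-dose category |
|---|---|---|---|---|
| 1 | 1/1 = 100% | 80% to 120% | 20% | <80% |
| 2 | 2/2 = 100% | 80% to 120% | 40% | <80% |
| 3 | 3/3 = 100% | 80% to 120% | 60% | <80% |
| 4 | 4/4 = 100% | 80% to 120% | 80% | 80% to 120% |
| 5 | 5/5 = 100% | 80% to 120% | 100% | 80% to 120% |

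A four-dose stop keeps its category under either definition.

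**Other dosing patterns.**
- Gaps before the last dose: doses on Days 1, 2, 3 and 5 give 4/5 = 80%; doses on Days 1 and 3 give 2/3 = 66.7%.
- All 5 packets over 6, 7 or 8 days: SAP 83.3%, 71.4% or 62.5%; planned-dose 100%. A full course over 7 days therefore ranks below a single-dose stopper.
- Over-use: 5 packets in 4 days gives 125% (planned-dose 100%); 4 packets in 3 days gives 133.3% (planned-dose 80%). The SAP ratio picks this up and used/5 does not.

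**Illustration for 100 patients.** The documents give no rate of early stopping, so the frequencies are assumed: m patients stop after 2 doses, everyone returns all packets, and the rest finish in 5 days. The SAP reports a mean of 100% with all 100 patients in 80% to 120%, whatever m is. The planned-dose mean is [100(100 − m) + 40m]/100, and the mean duration is [2m + 5(100 − m)]/100.

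| m | Planned-dose mean | Patients in 80% to 120% (planned-dose) | Mean duration (days) |
|---|---|---|---|
| 1 | 99.4% | 99 | 4.97 |
| 5 | 97.0% | 95 | 4.85 |
| 10 | 94.0% | 90 | 4.70 |

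In each case the minimum duration is 2 days, but Q1, median and Q3 are all 5.

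**Effect of the missing rule, m = 5.** If r of the 5 stoppers return every packet, the SAP mean is 100% on 95 + r patients. The planned-dose mean is (9500 + 40r)/(95 + r): 100% for r = 0, 98.2% for r = 3 and 97.0% for r = 5. The gap runs from 0 to 3.0 points.

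**The case against.** The strongest reply is that nothing here contradicts the protocol and little is hidden.

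- **The choice may be deliberate.** Protocol 9.5 sets no denominator, and protocol 11.6 promises only descriptive statistics. SAP section 11 can be read as reporting two things: how long patients were treated, and how regularly they dosed in that time. The category above 120% fits a rate, since used/5 cannot exceed 100% with 5 packets dispensed.
- **Early stops show elsewhere.** Duration of exposure and amount applied are summarised. Packets used, exposure and interruptions are listed. Protocol 10.5.2.1 asks that a local sign leading to discontinuation be reported as an AE, and SAP 14.3 tabulates TEAEs leading to treatment discontinuation.
- **Nothing depends on it.** There is one analysis population, no inference, and no endpoint that uses compliance.
- **Stops may be rare.** Protocol 5.2 says of the pivotal studies that "there were no treatment-related treatment-emergent serious AEs (TESAEs) or discontinuations due to a TEAE".
- **The 7-day course is not the planned case.** Packets come back on Day 5, and protocol 10.3.2 does not allow that visit to be skipped or repeated.

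Most of this stands as a limit on importance, and none of it changes the percentage or the category reported. The TEAE table misses stops for other reasons. The SAP specifies packets used only in a listing, not in a table. In the illustration with 5 stoppers, only the mean and minimum of duration move. The pivotal studies treated 25 cm² fields, so their experience may not carry over to 100 cm². The 7-day course is unplanned but possible, because protocol 9.5 provides for recording treatment delays.

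**Conclusion.** The concern holds. For a fixed 5-dose course, SAP 11.2 gives 100% to any gap-free early stopper who returns all packets, where planned-dose compliance is 20% to 80%. Stops after 1, 2 or 3 doses are placed in the wrong category relative to the planned course.

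The result rests on one packet per day, no gap before the stop, and return of all 5 packets. If stoppers do not return their packets, their compliance is missing and the discrepancy disappears. How many patients would be affected cannot be computed from the documents.

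The consequence is limited to the descriptive compliance tables, overall and by face or scalp. No safety or lesion-count result changes. It should be fixed because the reported figure is misleading as labelled and the correction is cheap.

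**What to change.** In SAP 11.2:

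1. Define compliance as used packets / 5 planned doses × 100, and keep the rule that it is missing unless all dispensed packets are returned.
2. Tabulate the number of packets used (1, 2, 3, 4, 5).
3. Keep the present packets-per-day ratio and its three categories as a second row, labelled as adherence while on treatment. Over-use and delayed courses then stay visible, which used/5 alone would not show.
4. Leave duration of exposure as its own summary under SAP 11.1.

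The cost is one formula, one relabelled row and one extra row in the table shells. Used packets are already in the eCRF, so no new data are needed. The only drawback is that reported compliance may look slightly less favourable.

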12 ANALYSES OF PRIOR AND CONCOMITANT MEDICATION

Medications will be coded according to the World Health Organization Drug Dictionary (WHO-DD) B3, March 2022.

Prior medications are defined as any medication started and discontinued prior to the first study treatment dosing. Concomitant medications are defined as any medication started on the same day than or after the first study treatment dosing, including those who started prior to the first study treatment date and continued past that date. See [Appendix 2](#) for handling of completely or partially missing dates and time for prior and concomitant medications.

Incidence of prior and concomitant medications will be tabulated by anatomical therapeutic chemical (ATC) Level 3 and standardized drug name using the safety population. A patient with the same medication taken multiple times will be counted only once for the corresponding standardized drug name. Similarly, if a patient has taken more than one medication within the same ATC level, then the patient will be counted only once for that ATC. Prior and concomitant medications will be sorted alphabetically by ATC level and within each ATC level, the standardized drug name will be presented by decreasing order.

Prior and concomitant medication information will be presented in a by-patient listing using the Safety population.

Actinic keratosis treatment non-drug therapies and procedures during the study will be provided in a listing.

